# 6.4 6-Minute Walk Test

Observed values and changes from baseline in the total distance walked during the 6-minute walk test will be summarized for ambulatory subjects only, if applicable.

The observed values for ambulatory subjects will be displayed in subject listings.

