#### Efficacy

The following efficacy outcome measures will be performed at Months 3 and 6 unless otherwise specified: PUL 1.2, spirometry, 6MWT when deemed appropriate by the Investigator, and cardiac MRI.

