# 11.5. 6-Minute Walk Test

Subjects assessed by the Investigator as capable of performing the 6MWT will do so on Day 1 and the protocol-specified follow-up visits. Subjects unable to perform the 6MWT on Day 1 will not be required to perform the test at any subsequent visit. Detailed information on performing the 6MWT are found in the trial MOP.

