#### 14.6.2. Missing Data

There are no plans for imputation of missing data. The reasons for missing data will be documented. Sensitivity analyses, however, may be performed using various assumptions for missing data to assess the impact on summary results.

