#### 2.2.2 Exploratory Efficacy Endpoints

The *exploratory endpoints* include the change from baseline to each assessment timepoint for the following assessments:

- All subjects
  - Mid-level (elbow) dimension of the Performance of the Upper Limb (PUL) 1.2
  - Mid- and distal-level (elbow) dimension of the PUL 1.2
  - High-level (shoulder) dimension of the PUL 1.2
  - Left ventricular structure and function, as assessed by cardiac MRI, including regional systolic left ventricular wall thickening, ejection fraction, end-diastolic volume, end-systolic volume, stroke volume, regional wall thickness, and circumferential strain
  - Slow vital capacity (SVC), forced expiratory volume in one second (FEV1), forced vital capacity (FVC), peak expiratory flow (PEF), maximum inspiratory pressure (MIP), maximum expiratory pressure (MEP), peak cough flow (PCF), and inspiratory flow reserve (IFR)
- Ambulatory subjects only
  - 6-Minute Walk Test (6MWT)

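### SAP 6.4 does not say when ambulatory status is set or how a Day 1 walker who later loses walking is scored; if that subject is left missing, the mean 6MWT change is too high

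*SAP*

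**What the plan says.** The 6MWT is an exploratory endpoint for ambulatory subjects. SAP 2.2.2 says that the exploratory endpoints "include the change from baseline to each assessment timepoint for the following assessments", and SAP 6.4 says that the distance walked "will be summarized for ambulatory subjects only, if applicable". Neither section gives the time at which a subject counts as ambulatory.

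On who is tested, the protocol speaks in three places:
- Protocol 11.5: "Subjects assessed by the Investigator as capable of performing the 6MWT will do so on Day 1 and the protocol-specified follow-up visits". Its one written exemption is "Subjects unable to perform the 6MWT on Day 1 will not be required to perform the test at any subsequent visit". It sends further detail to the Manual of Procedures, which is not among the documents reviewed.
- Protocol Synopsis, Efficacy paragraph: the Month 3 and Month 6 measures include "6MWT when deemed appropriate by the Investigator".
- Protocol Table 3 (repeated in SAP Appendix B): footnote 10 limits the whole 6MWT row, Day 1 and both follow-up visits, to ambulatory subjects.

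On missing values, Protocol 14.6.2 states: "There are no plans for imputation of missing data". It adds that reasons will be documented, and then: "Sensitivity analyses, however, may be performed using various assumptions for missing data to assess the impact on summary results". SAP 4.3 has rules for dates, adverse event attributes, medical history and medications, but none for missing efficacy values.

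**The concern.** In a progressive disease, the worst result on a walking test is to become unable to do it. Both documents describe eventual wheelchair dependence, in most cases between 12 and 15 years of age (Protocol 5.1, SAP 1), so a loss during follow-up is foreseeable in any subject who enters walking. If such a subject is not tested, he has no change value, and the mean is taken over the subjects who kept walking. The worst outcome then counts for nothing, and the summary looks better than the course of the group that started.

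With no concurrent control arm, there is no second mean subject to the same loss. With at most 10 subjects, of whom an unstated number can walk, a single loss could move the mean a long way.

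**Working it through.** **No figure to reproduce.** The documents give no 6MWT standard deviation, expected change or number of walkers. Up to 10 subjects (Protocol 7.3) is a cap without a calculation.

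**Step 1: what happens to a Day 1 walker who loses walking.** Two things are left open, when status is set and how the loss is recorded. The four combinations are:

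| Ambulatory status set | Loss recorded as 0 m | Loss recorded as missing |
|---|---|---|
| At Day 1 | stays in the mean | no change value, drops out |
| At each visit | outside the set, drops out | outside the set, drops out |

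Only a Day 1 set with 0 m recorded keeps him in. If he is missing, he drops out whichever time is used for status.

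**Step 2: size of the shift.** Let n subjects walk on Day 1 and k of them lose walking. B is the mean baseline distance of those k, and m is the mean change of the other n − k. Assume no values are missing for other reasons.

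- Observed-case mean = m
- Mean with 0 m entered for the k subjects = ((n − k)m − kB)/n
- Difference = m − ((n − k)m − kB)/n = (k/n)(m + B)

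The difference is positive whenever k > 0 and m > −B, that is, unless the remaining walkers lose on average at least as much distance as B. It is 0 when k = 0.

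**Step 3: illustration.** These inputs are assumptions, not figures from the documents: k = 1, B from 100 to 300 m, m from −30 to +30 m.

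| Day 1 walkers (n) | Smallest: (−30 + 100)/n | Largest: (30 + 300)/n |
|---|---|---|
| 10 | 70/10 = 7 m | 330/10 = 33 m |
| 5 | 70/5 = 14 m | 330/5 = 66 m |
| 3 | 70/3 = 23 m | 330/3 = 110 m |

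**Step 4: what a worst-rank median does.** Assume 4 walkers, three with changes of −10, −20 and −30 m and one who loses walking.

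- Observed-case mean: −60/3 = −20 m. Observed-case median: −20 m.
- Mean with 0 m entered, baseline 150 m: (−60 − 150)/4 = −52.5 m.
- Mean with 0 m entered, baseline 350 m: (−60 − 350)/4 = −102.5 m.
- Median with the lost walker ranked worst: midway between −30 and −20, which is −25 m.

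The 0 m mean depends heavily on the lost walker's baseline. The worst-rank median does not use it, and remains a number as long as fewer than half of the Day 1 walkers are lost.

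**The case against.** A reader might infer that the SAP restricts the summary to subjects who are still walking at each visit. The text does not say so. SAP 6.4 is silent on timing, and Protocol 11.5 leans toward a Day 1 set: those capable are tested on Day 1 and at follow-up, and only inability on Day 1 is an exemption. This objection stands as far as it goes. It does not close the gap, because the synopsis and footnote 10 make follow-up testing conditional, and a Day 1 subject who is not tested still has no change value.

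A reader might also infer that the loss could not be seen anywhere in the output. That is not so. SAP 4 gives n with every continuous summary, SAP 5.4 reports how many could do the test at baseline, SAP 5.2 lists missed efficacy assessments, and SAP 5.5 lists wheelchair status by subject. In a trial this small, a careful reader could find the subject. But the fall in n carries no reason, the missed-assessment listing names only the visit or assessment, and none of these outputs is tied to the 6MWT table.

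Two further points count on the other side. The Manual of Procedures may state how inability is recorded, and Protocol 14.6.2 allows sensitivity analyses. The first cannot be checked here, and the second is optional with no assumptions stated.

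Finally, in the four-walker example the proposed median moves only from −20 to −25 m. That is fair: the worst-rank median is a modest correction, and the count of subjects unable to walk carries most of the information.

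**Conclusion.** The concern holds as a gap in specification with a conditional consequence. The plan leaves open when ambulatory status is set and how a later loss of walking is scored. If such a loss occurs and is left missing, the observed-case mean change is too high by (k/n)(m + B), taking 0 m as the reference. It would be going too far to say that the 6MWT result is biased: that needs at least one loss within about 6 months, and the shift is zero if nobody loses walking or if the loss is entered as 0 m in a Day 1 set.

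The direction follows from the algebra. The sizes, 7 to 33 m with 10 walkers and 23 to 110 m with 3, are illustrations on assumed inputs. The weight is limited: the endpoint is exploratory, the trial is single-arm, and Protocol 14.1 sets no formal hypothesis and treats p-values as nominal. It is a minor point, worth settling because it is cheap and best decided before the data are seen.

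**What to change.** In SAP 6.4:

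1. Define the 6MWT set, within ITT and within PP, as all subjects who performed the test on Day 1.
2. At Months 3 and 6, report the number and percentage of that set unable to perform the test because of disease, separately from tests missed for other reasons. State that the denominator is the Day 1 performers, since the SAP 4 default bases percentages on subjects with available data.
3. Beside the observed-case mean, give the median change with the subjects unable because of disease ranked worst. If half or more are unable, say so in place of a number.

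The Medical Status Questionnaire at Day 1, Month 3 and Month 6 and the documented reasons for missing data should supply what is needed, so trial conduct does not change. The cost is a few lines of SAP wording and one extra row. The downside is a second summary in very few subjects. If nobody loses walking, the count is zero and the two summaries agree, apart from any tests missed for other reasons.

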# 7 SAFETY ANALYSES

Listings and summaries of the safety parameters will be done for the Safety population. An overall summary table will be presented that summarizes the primary safety endpoints. Safety parameters are described below.

# 7.1 Adverse Events

Adverse events will be coded using the Medical Dictionary for Regulatory Activities (MedDRA) coding system (Version 21.0). Potential primary safety endpoints, described in Section 2.2.1, will be adjudicated by an independent Clinical Events Committee (CEC).

The following AEs are defined as treatment-emergent AEs (TEAEs):

- AEs occurring after the initiation of the IV catheter placement for the initial dose of IP; or
- AEs with a completely missing start date, or similarly, AEs that started the same month and year as IP administration but with missing start day.

Subject listings of all adverse events as reported will be provided. A separate listing will be done for TEAEs as adjudicated by the CEC. All summary tables will be reported using as adjudicated by the CEC.

An overall summary table will be presented by treatment group that summarizes subject with the following:

- Any TEAEs
- TEAEs by maximum severity
- TEAEs and serious TEAEs by greatest degree of relationship to IP or IP administration
- TEAEs and serious TEAEs by greatest degree of relationship to IP only
- TEAEs and serious TEAEs by greatest degree of relationship to IP administration only
- Serious TEAEs
- TEAEs leading to study discontinuation, and
- TEAEs leading to death

In addition, TEAEs will be summarized overall by system organ class and preferred term and by severity and by relationship to the IP and IP administration procedure.

Deaths, AEs that resulted in study discontinuation, serious adverse events (SAEs), serious TEAEs and AEs within 24 hours of IP administration will be listed and summarized.

Summaries of 'related' TEAEs, will include TEAEs with a reported relationship to IP and/or IP administration of "Probable" or "Possible". Adverse events will be displayed by MedDRA System Organ Class and Preferred Terms, with subjects who have the same adverse event counted only once for that event and with subjects who have more than one adverse event within a System Organ Class counted only once in that System Organ Class. The numbers and percentages of subjects reporting an event as well as the number of events that were reported will be displayed.

Frequency tables will be ordered by decreasing percentage in the SOCs, then alphabetically. Within each SOC, PTs will be ordered by decreasing percentage then alphabetically.

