#### 13.2.1.2. Serious Adverse Event (SAE)

An AE is considered "serious" if, in the view of either the Investigator or Capricor, it results in any of the following outcomes:

- Death
- Life-threatening adverse event

- Inpatient hospitalization or prolongation of existing hospitalization
- Persistent or significant incapacity or substantial disruption of the ability to conduct normal life functions
- Congenital anomaly/birth defect

Important medical events that may not result in death, be life-threatening, or require hospitalization may be considered serious when, based upon appropriate medical judgment, they may jeopardize the subject and may require medical or surgical intervention to prevent one of the outcomes listed in this definition.

Examples of such medical events include bronchospasm requiring intensive treatment in an emergency room or at home, blood dyscrasias, or convulsions that do not result in inpatient hospitalization, or the development of drug dependency or drug abuse.

Complications that occur during a hospitalization are AEs. When the hospitalization is prolonged due to the complication or the complication fulfills any other serious criteria, the event is reported as an SAE. Hospitalization for elective treatment of a pre-existing condition that did not worsen from baseline is not considered an SAE.

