#### **13.2.2.** Relationship to Investigational Product

The Investigator will assess the relationship (causality) of an AE to the investigational product and administration procedure.

Causality will be defined as follows:

- *Probable*: adverse events that, after careful medical evaluation, are considered with a high degree of certainty to be related to the investigational product or administration procedure. The following characteristics will apply:
  - A reasonable temporal relationship exists between the event and the investigational product or administration procedure, and
  - The event is a known reaction to the investigational product or administration procedure, which cannot be explained by an alternative etiology commonly occurring in the population/individual.
- **Possible**: adverse events that, after careful medical evaluation, do not meet the criteria for a probable relationship to the investigational product or administration procedure, but for which a connection has reasonable certainty. The following characteristics apply:
  - The event occurs after exposure to the investigational product or administration procedure, and
  - The event is not a known reaction to the investigational product or administration procedure, but cannot be explained by a commonly occurring alternative etiology, or
  - In the absence of a temporal relationship, the event cannot reasonably be explained by an alternative etiology.
- *Unlikely*: adverse events that, after careful medical evaluation, do not meet the criteria for possible or probable relationship to investigational product or administration procedure and for which a connection is unlikely. The following characteristics will apply:
  - The event does not follow a reasonable temporal sequence from administration of the investigational product or administration procedure, or
  - May be explained by commonly occurring alternative etiology in the population/individual, or
  - May have been produced by environmental factors, and there is no apparent pattern of response to the investigational product or administration procedure.

An adverse event will be reported as "related" when causality is evaluated by an Investigator as probably or possibly related to the investigational product and/or the administration procedure.

Related adverse events indicate a potential cause-and-effect relationship between the investigational product and/or administration procedure and the occurrence of the adverse event.

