# 2.2 Study Endpoints

#### 2.2.1 Primary Safety Endpoint

The *primary safety endpoints* include the incidence of the following from baseline through the 6-month timepoint:

- Acute respiratory decompensation within 2 hours following Investigational Product (IP) administration
- Hypersensitivity reaction
  - Hypersensitivity reaction is defined as a clinical syndrome including, but not limited to, fever, leukocytosis, or rash with onset  $\leq 2$  hours post infusion and lasting < 24 hours, in the absence of clinical signs of concomitant infection.
- All-cause mortality
- Serious adverse events (SAEs)
- Treatment-emergent adverse events (TEAEs) related to IP or administration procedure
- Immune sensitization syndrome
  - Immune sensitization syndrome shall be defined as:

(a) clinical signs and symptoms consistent with systemic inflammation (e.g., fever, leukocytosis, rash, or arthralgia) with onset  $\geq 24$  hours post infusion and the absence of clinical signs of concomitant infection,

AND

(b) elevation of anti-human leukocyte antigen (HLA) antibodies against the donor cells (i.e., DSAs), detected  $\leq$  30 days following onset of syndrome, of

- (i)  $\geq$  2000 mean fluorescent intensity (MFI) if baseline MFI  $\leq$  1000, or
- (ii)  $\geq$  2 times baseline otherwise

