#### 7.1.1 Clinical Events Committee (CEC)

To apply some level of consistency and standardization, all potential primary safety endpoints will be adjudicated by a CEC. The CEC can combine AEs reported separately into a single AE, can change the event description (i.e., the term used to report the AE), and can change the status of the reported event to a non-AE.

Any adjudicated event, including changed event descriptions, will be MedDRA-coded.

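### All AE summary tables rest on CEC-adjudicated events, so a reported SAE or related TEAE that the CEC makes a non-AE appears only in a listing

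*SAP*

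**What the plan says.** SAP 2.2.1 names the primary safety endpoints as incidences from baseline to the 6-month timepoint. They include SAEs and "Treatment-emergent adverse events (TEAEs) related to IP or administration procedure".

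SAP 7.1.1 sets the scope of adjudication: "all potential primary safety endpoints will be adjudicated by a CEC". It gives the CEC three powers: to combine separately reported AEs into one, to change the event term, and a third under which it "can change the status of the reported event to a non-AE".

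SAP 7.1 then says where each version of the data is shown. For reported data: "Subject listings of all adverse events as reported will be provided". A separate listing covers TEAEs after adjudication. For tables: "All summary tables will be reported using as adjudicated by the CEC". The same section bases summaries of related TEAEs on the relationship as reported, without saying by whom.

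The protocol places the underlying judgements elsewhere. Under 13.2.1.2 an AE is serious if, "in the view of either the Investigator or Capricor, it results in any of the following outcomes". Under 13.2.2 an AE is reported as related "when causality is evaluated by an Investigator as probably or possibly related to the investigational product" or the procedure.

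**The concern.** Two primary safety endpoints depend on judgements that the protocol gives to the Investigator, or for seriousness to the Investigator or the sponsor. Under the SAP, an event that was reported as serious or related and then made a non-AE is counted in no table. No as-reported table is planned beside the adjudicated ones, and no listing shows what the CEC changed.

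The tabulated incidence could therefore be lower than what sites reported, and no table would show the difference. The trial has one arm, so there is no control rate against which a low figure would look odd. Enrolment is capped at 10, so a single decision is visible in the percentage.

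**Working it through.** The documents state no power, precision or reclassification figure for this point, so there is nothing of the plan's own to reproduce. The check is mainly textual, followed by simple arithmetic.

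**Step 1: which events reach the CEC.** SAP 2.2.1 makes SAEs and related TEAEs primary safety endpoints. SAP 7.1.1 and protocol 15.2 send all potential primary safety endpoints to the CEC. So every reported SAE and every reported related TEAE is within its scope. AEs that are neither serious nor related are generally outside it. The SAP does not say how these enter tables described as adjudicated; I assume as reported.

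**Step 2: what each CEC action does to the outputs.**

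- *Combined:* the events remain as one AE in the adjudicated data. The number of events falls, but the subject still has an event.
- *Renamed:* the event stays under a new term. Its system organ class or preferred term row may change.
- *Made a non-AE:* the event leaves the adjudicated TEAE listing and every summary table. It stays in the as-reported listing.

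Only the third action removes a reported event altogether from the tables.

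**Step 3: whether other wording restores it.** The rule that related TEAEs are summarised by reported relationship concerns an attribute of TEAEs already in the table. It does not bring back an event that is no longer an AE. It does suggest that events which stay in the tables may be classified by the reported relationship. SAP 7.1.1 names no CEC power to change causality or seriousness. The exposure is therefore mainly non-AE decisions.

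**Step 4: size, as an illustration.** Inputs: up to 10 subjects (protocol 14.2); one subject whose only SAE, or only related TEAE, is made a non-AE (hypothetical).

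Change in tabulated incidence = 100/n percentage points.

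- n = 10: 100/10 = 10.0 points, so 1/10 (10%) becomes 0/10 (0%).
- n = 8 (assumed): 100/8 = 12.5 points.
- n = 6 (assumed): 100/6 = 16.7 points.

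For context, the exact (Clopper-Pearson) 95% interval for 1/10 is 0.3% to 44.5%. For 0/10 it runs from 0% to 1 − 0.025^(1/10) = 30.8%. These overlap widely, and the SAP plans only counts and percentages for AEs. What changes is whether the table shows an event at all; the precision of the estimate is poor either way.

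**The case against.** The strongest reply is that making an event a non-AE may be exactly what the protocol calls for. Seriousness and causality are attributes of something that must first be an AE. Protocol 13.2.1.1 excludes procedures as such, social admissions, stable fluctuation of existing conditions and expected progression of DMD. Protocol 13.2.3 says that individual signs and symptoms of a diagnosed event are not to be reported separately. An independent committee that applies those rules consistently is doing its job. This stands, and it is why the adjudicated tables should stay.

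The transparency already planned is also considerable. As-reported AEs are listed, and SAP 7.1 lists as well as summarises deaths, SAEs and AEs within 24 hours of administration. Protocol 14.1 requires a full data listing, and 13.2.4 sends SAEs to the DSMB separately. With at most 10 subjects a determined reader could count by hand. The trial has no formal hypotheses, and its primary objective is to provide the product. All of this limits the harm. It does not put the reported counts into a table, and it does not state which CEC action explains a difference between the two listings.

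A reader might infer more than the documents support:

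- *That the SAP contradicts the protocol.* Protocol 14.4.1 asks that endpoints and observed AEs be documented, reported and summarised. It does not expressly require as-reported tables.
- *That combined events vanish from the adjudicated listing.* SAP 7.1.1 says they become a single AE, so the event remains.
- *That combining could move an event to before catheter placement and cost it treatment-emergent status.* No passage says which onset date a combined event takes, or that a non-serious event before catheter placement would be before the CEC at all. This is speculation.

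**Conclusion.** The point holds as a reporting gap of minor severity. Under SAP 7.1 and 7.1.1 together, a reported SAE or related TEAE that the CEC makes a non-AE is absent from every AE summary table and survives only in the as-reported listing and, for SAEs, in reports to the DSMB. With 10 subjects, one such decision can turn a tabulated 10% into 0%.

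That figure rests on one hypothetical decision affecting a subject's only event of that type; the documents do not say how often this would happen. Nothing in the documents suggests that the CEC would decide wrongly or with bias.

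**What to change.** In SAP 7.1:

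1. Keep the adjudicated tables as planned.
2. In the overall AE summary, add as-reported numbers and percentages of subjects with any TEAE, with SAEs/serious TEAEs, and with related TEAEs by the Investigator's assessment.
3. State that the reported relationship used for the related-TEAE summaries is the Investigator's.
4. Add one listing of each CEC change, giving the type of change (combined, renamed, made a non-AE) with the reported and adjudicated terms.

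The cost is SAP wording, three extra entries in one table, and one listing. No new data are needed, assuming that the CEC's record of each decision links reported to adjudicated events. The downside is two sets of counts, which the study report will have to explain.
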